## **1. OBJECTIVES**

### **1.1 Primary Objectives**

1.1.1 *To assess whether use of preservative free artificial tears following radioactive iodine administration will lower the level of radioactive iodine in the tears of patients treated with radioactive iodine for thyroid carcinoma.*

### **1.2 Secondary Objectives**

1.2.1 *Secondary objective is to deduce whether artificial tears would be an effective preventative intervention to decrease the risk of developing nasolacrimal duct stenosis, which has been associated with radioactive iodine administration. Patients will be monitored over time for development of nasolacrimal duct stenosis symptoms, such as epiphora or tear duct infections.*

## **2. BACKGROUND**

### **2.1 Study Disease(s)**

*Radioactive iodine is commonly used for the treatment of thyroid carcinoma. The association of radioiodine therapy for the treatment of differential thyroid carcinoma with nasolacrimal duct dysfunction has been well documented in many research studies. Doses of 150 mCi or more, which are frequently used in the treatment of thyroid carcinoma, have been found to significantly increase a patient's risk of developing nasolacrimal duct obstruction. Prior studies have estimated the incidence of radioactive iodine associated nasolacrimal duct obstruction to be around 3 to 4.6%.*

*Prior case reports have documented radioactive iodine detection in the tears of patients following radioiodine ablation for thyroid cancer. A likely mechanism is that the radioactive iodine is taken up from the tears by the stratified columnar epithelial cells of the lacrimal sac and nasolacrimal ducts, leading to inflammation and fibrosis, and subsequent stenosis and obstruction of the lacrimal lumen over time.*

*The purpose of this study is to explore whether administration of preservative free artificial tears will decrease the level of detectable radioiodine in the tears and nasolacrimal duct system of patients undergoing radioiodine therapy for differential thyroid carcinoma. There are no current studies analyzing what threshold of radioactive iodine in tears is considered to be less likely to cause nasolacrimal duct stenosis. Given that radioactive iodine uptake by the epithelial cells lining the lacrimal sac is the likely cause of subsequent fibrosis and obstruction, the hypothesis is that decreasing the concentration of radioactive iodine in tears as much as*

*possible with artificial tears will thus decrease the risk of developing nasolacrimal duct obstruction. We believe that the lower the radioactive iodine level in tears, the lower the risk of developing nasolacrimal duct obstruction.*

*We will recruit a total of 5 patients who wear bilateral disposable contact lenses, have them self-administer preservative free artificial tears in the right contact-wearing eye (left contact-wearing eye will receive no tears), and obtain their tear-containing contact lenses from both eyes and measure radioiodine levels.*

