#### **5.1.1 Primary and Secondary Endpoint**

*The primary endpoint will be to assess for the development of nasolacrimal duct obstruction over two years in 8 month intervals. Every 8 months, each patient will be assessed in the ophthalmology clinic for nasolacrimal duct dysfunction via tear duct irrigation. The secondary endpoint is the level of radioactive iodine measured in the tears of patients collected via their contact lenses. Patients will be asked to store their daily contact lenses in sterile container for subsequent radioactive iodine level analysis via a well counter in the Nuclear Medicine department. These contact lenses will be collected at their 1 week routine appointment with Nuclear Medicine.*

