## **6. STATISTICAL CONSIDERATIONS**

*Radioactive iodine levels from the right contact lenses of patients will be compared to that of the left contact lenses that did not have exposure to artificial tears. The data gathered will be analyzed by the statistics personnel in the department of Ophthalmology.*

*In more detail: the area under the curve (AUC) of all four days for each patient was calculated as the sum of the four trapezoid areas under the I-131 exposure values. To meet the normality assumption, I-131 activities and AUCs were logarithmically transformed to obtain geometric mean I-131 activities of each day and geometric mean AUCs. The Shapiro-Wilk test was used to evaluate the normal assumption for logarithmically transformed AUCs (log-AUCs). The 95% confidence intervals (CI) of the AUCs were constructed for the right experimental eyes and left control eyes, assuming normality for log-AUCs, which were compared between the two groups using paired t-tests. Statistical analyses were conducted using R version 4.1.2 (R Project for Statistical Computing, [www.r-project.org](http://www.r-project.org)). Two sided  $p < 0.05$  was considered statistically significant.*

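### The drops always go in the right eye and the left is always the control, so the planned paired test cannot separate the tear effect from a systematic right-left difference

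*Combined protocol and SAP*

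**What the plan says.** Section 2.1 sets the sample and the allocation: "We will recruit a total of 5 patients who wear bilateral disposable contact lenses", and they "self-administer preservative free artificial tears in the right contact-wearing eye (left contact-wearing eye will receive no tears"). Section 5.1 gives the drop schedule without naming an eye.

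Section 6 carries the same fixed roles into the analysis: "Radioactive iodine levels from the right contact lenses of patients will be compared to that of the left contact lenses". The four-day AUCs are log-transformed, confidence intervals are built for the "right experimental eyes and left control eyes", and the two are tested by paired t-test, two-sided at 0.05.

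Section 1.1 makes this the comparison of main interest, since the primary objective is whether the drops "will lower the level of radioactive iodine in the tears of patients treated with radioactive iodine for thyroid carcinoma". Section 5.1.1 nevertheless labels lens activity the secondary endpoint. Patients give the drops themselves and keep the lenses themselves: "Patients will be asked to store their daily contact lenses in sterile container for subsequent radioactive iodine level analysis".

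The sections available for review contain no randomisation or alternation of the treated side, no side term, no drop-free pair of lenses for comparison, and no reason for choosing the right eye.

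**The concern.** In a paired-eye design each patient is their own control. That removes differences between patients, such as administered activity. It does not remove a difference between right and left that runs the same way across patients. When treatment is always on the right, treatment and side are the same variable, and such a difference goes straight into the estimated effect.

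It could act in either direction. If untreated right lenses tend to carry less activity, the study could report a benefit that the drops did not produce. If they tend to carry more, a real benefit could be hidden. A fixed order of handling the lenses or the patient's handedness are conceivable sources, but these are assumptions; the documents report no such difference. What the documents do show is that drops and lenses are handled at home, so equal handling of the two sides is assumed rather than controlled.

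**Working it through.** The plan gives no SD, effect size or power figure, so there is nothing of its own to reproduce.

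**Inputs from the documents.** 5 pairs and the right eye always treated (Section 2.1); paired t-test on log-AUC, two-sided 0.05 (Section 6).

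**Step 1: what the contrast estimates.** For patient *i* write

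D_i = log AUC(right) − log AUC(left) = ρ + τ·s_i + e_i,

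where τ is the tear effect, ρ the systematic side difference, and s_i is +1 if the right eye is treated and −1 if the left is. Under the plan s_i = +1 for all five, so the design matrix with columns s and 1 has rank 1 and the mean of D estimates τ + ρ. With a 3:2 split the rank is 2 and τ can be estimated separately from ρ. Right-left differences that vary at random between patients belong to e_i and cause no bias.

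**Step 2: false positives when τ = 0.** Noncentral t with df = 4, critical value 2.776, noncentrality = (ρ/SD)·√5. SD is that of the paired log-AUC differences, and the values of ρ are assumed. If either direction of ρ is equally likely, the chance of a false claim of benefit is half the rejection rate.

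| ρ/SD | two-sided rejection | false claim of benefit |
|---|---|---|
| 0 | 5.0% | 2.5% |
| 0.25 | 7.2% | 3.6% |
| 0.5 | 14.1% | 7.0% |
| 0.75 | 25.4% | 12.7% |
| 1.0 | 40.1% | 20.1% |

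**Step 3: the same on the activity scale.** Suppose right-eye activity is systematically 10% lower, so ρ = ln 0.9 = −0.105. For a log-scale SD of 0.1, 0.2, 0.3 and 0.5, rejection with no tear effect is 43.6%, 15.1%, 9.4% and 6.6%. For 20% lower it is 95.4%, 47.6%, 25.0% and 12.2%.

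**Step 4: masking.** Take an assumed tear effect of 1.5 SD opposed by the side difference, so the net effect is 1.5 − ρ/SD. Power is 71.1% with no side difference and 56.2%, 40.1%, 25.4% and 14.1% at 0.25, 0.5, 0.75 and 1.0 SD.

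**Step 5: the treated eye randomised 3:2, majority side random** (1,000,000 simulated trials per setting; mean bias about zero).

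| ρ/SD | size, plain paired t | power at 1.5 SD, plain paired t |
|---|---|---|
| 0 | 5.0% | 71.1% |
| 0.25 | 4.6% | 68.4% |
| 0.5 | 3.5% | 60.8% |
| 0.75 | 2.3% | 49.3% |
| 1.0 | 1.3% | 36.6% |

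Adding a side term gives df = 3, critical value 3.182 and variance factor (1/3 + 1/2)/4 = 0.2083, against 1/5 = 0.2. Its size is 5.0% and its power at 1.5 SD is 60.2% whatever ρ is. The two tests have about equal power near ρ = 0.5 SD.

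Independent coin tosses per patient are less suitable than 3:2: the plain test's size then ranged from 4.9% to 7.0% in simulation. An exact sign-flip test is not an alternative with 5 pairs, because its smallest two-sided p is 2/32 = 0.0625.

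**Step 6: mixed-up eyes.** If one patient of five treats the wrong eye throughout, the mean becomes (4 × 1.5 − 1.5)/5 = 0.9 SD and the spread grows. Power for a 1.5 SD effect drops to 6.2%.

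**The case against.** The strongest reply is that no side difference is documented. Both eyes share one patient and one radioiodine administration, and Section 3.2 excludes ocular or lacrimal trauma and lacrimal drainage disease. The side difference may be small: 10% with a log SD of 0.3 to 0.5 gives rejection of only 9.4% to 6.6%. This stands, and it is why every size given here is conditional. It does not rescue the design, because the plan offers no way to check the assumption.

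A second reply is that the daily means hold some information. By the Section 5.1 schedule drops fall from about 16 on Day 1 (8 + 8) to 12, 4 and 2, so a constant side offset would persist to Day 4 while a drop effect should fade. That is partly right, and it is why the point is limited to the planned AUC test. The separation needs a constant offset and an effect that tracks drop count without carry-over, and Section 6 plans no by-day test.

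Third, extra touching or lens displacement caused by giving drops follows treatment, not side, and randomisation would not remove it. That is correct. Only differences tied to right or left as such are cured.

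Fourth, one uniform instruction is easier to follow at home. If each patient had an assumed 5% risk of swapping eyes, the chance of at least one swap would be 1 − 0.95^5 = 23% and power about 56%, the same loss as from an opposing 0.25 SD side difference. This is a real cost. Swaps can also occur under the fixed rule, so only the added risk counts, and labelling can reduce it.

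Finally, Section 6 is written partly in the past tense, so the data may already exist. In that case only the reporting remedy applies.

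**Conclusion.** The concern holds. The aliasing of treatment with side is certain from Sections 2.1 and 6 and needs no numerical assumption. Its consequence is unknown: none if untreated eyes do not differ by side, and substantial if the difference reaches about half an SD of the paired differences or more. The side differences, the SDs and the 1.5 SD tear effect in the calculations are all assumed. The point should be acted on because it bears on the comparison that answers the primary objective and the remedy is cheap. It does not show that a result from this design would be wrong.

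**What to change.** **If lenses have not yet been collected.**

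- Randomise the treated eye per patient from a pre-generated list of five, split 3:2 with the majority side chosen at random.
- In Sections 2.1 and 6 replace right and left with treated (assigned) and control eye, and have Section 5.1 refer to the assigned eye.
- In Section 6 define the outcome as treated minus control log-AUC. Make the plain paired t-test the main analysis: no side difference is documented, and under 3:2 its size did not exceed 5%, beyond simulation error, at any side difference examined. Pre-specify the same test with a side term (df = 3) as a sensitivity analysis.
- Write the assigned eye on the drops and the lens containers, and record the eye actually treated.

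**If lenses have already been collected.** State that the result is a right-left contrast, and that it equals the tear effect only if untreated eyes do not differ systematically by side.

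**Cost.** A five-line list, wording changes and labels. With no side difference the plain test keeps its full 71% power for a 1.5 SD effect. With one it becomes conservative, with power of 61% at 0.5 SD and 37% at 1 SD. The side-term test gives up about 11 points (71% to 60%) when there is no side difference. The practical cost is the added chance of mixed-up eyes.

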### **3. PATIENT SELECTION**

#### **3.1 Eligibility Criteria**

*There will be no age restriction to this study.*

*Inclusion Criteria (must meet all below to be recruited):*

- 1. Radio-iodine therapy for thyroid cancer*
- 2. Radioiodine therapy  $\geq 150\text{mCi}$*
- 3. Patient wears contacts on both eyes*

#### **3.2 Exclusion Criteria**

*Exclusion Criteria:*

- 1. Use of eye drops, other than artificial tears*
- 2. History of ocular/lacrimal gland trauma*
- 3. History of lacrimal drainage disease: canaliculitis, dacryocystitis*
- 4. Prior radiotherapy*
- 5. Current or prior use of chemotherapy drugs (i.e. 5-fluorouracil, docetaxel)*
- 6. Medical conditions that predispose to NLD stenosis*
  - a. Sarcoid*
  - b. Granulomatosis with polyangiitis*
  - c. Chronic lymphocytic leukemia*

### **4. REGISTRATION PROCEDURES**

*Patients will be identified through the Nuclear Medicine and/or Endocrine department. Patients who meet all inclusion criteria will be asked whether they would like to participate in the study.*

## **5. TREATMENT AND/OR IMAGING PLAN**

### **5.1 Agent Administration**

*Artificial tears are the study agent of interest and bear minimal risks and side effects. The regimen for self-administration of artificial tears is as follows: on Day 1, patients will self-administer artificial tears every 15 minutes for 2 hours followed by every 30 minutes for 4 hours. On Day 2, patients will self-administer artificial tears every 1 hour for 12 hours. On Day 3, patients will self-administer artificial tears four times that day. On Day 4, patients will self-administer tears twice that day. Patients will be instructed to wear their contact lenses throughout their waking hours. The rationale for this proposed regimen is to dilute the radioactive iodine from the tear ducts with frequent administration of artificial tears. Zettinig et al showed that radioiodine levels are highest in tears on the first day and significantly decrease over 4-5 days, which serves as the underlying rationale for having patients self-administer artificial tears for four days.*

*Routine whole body scintigraphy (WBS) and/or single photon emission computed tomography (SPECT-CT) will be obtained around 1 week post-radioiodine as part of the routine care patients receive after having radioiodine administration for treatment of thyroid cancer. No adjustments will be made to this routine imaging that patients receive. We will analyze the routine images for localization of radioiodine in the intranasal and nasolacrimal duct regions.*

#### **5.1.1 Primary and Secondary Endpoint**

*The primary endpoint will be to assess for the development of nasolacrimal duct obstruction over two years in 8 month intervals. Every 8 months, each patient will be assessed in the ophthalmology clinic for nasolacrimal duct dysfunction via tear duct irrigation. The secondary endpoint is the level of radioactive iodine measured in the tears of patients collected via their contact lenses. Patients will be asked to store their daily contact lenses in sterile container for subsequent radioactive iodine level analysis via a well counter in the Nuclear Medicine department. These contact lenses will be collected at their 1 week routine appointment with Nuclear Medicine.*

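### Section 5.1.1 makes two-year duct obstruction the primary endpoint, reversing the Section 1 objectives; Section 6 gives it no analysis, and 5 patients can say almost nothing about it

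*Combined protocol and SAP*

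**What the plan says.** The document ranks its two outcomes in opposite orders.

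- **Section 1.1, primary objective:** "To assess whether use of preservative free artificial tears following radioactive iodine administration will lower the level of radioactive iodine in the tears".
- **Section 1.2, secondary objective:** "Secondary objective is to deduce whether artificial tears would be an effective preventative intervention to decrease the risk of developing nasolacrimal duct stenosis". The same section adds: "Patients will be monitored over time for development of nasolacrimal duct stenosis symptoms, such as epiphora or tear duct infections".
- **Section 5.1.1, primary endpoint:** "The primary endpoint will be to assess for the development of nasolacrimal duct obstruction over two years in 8 month intervals". The method follows: "Every 8 months, each patient will be assessed in the ophthalmology clinic for nasolacrimal duct dysfunction via tear duct irrigation".
- **Section 5.1.1, secondary endpoint:** "The secondary endpoint is the level of radioactive iodine measured in the tears of patients collected via their contact lenses".

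Section 6 describes one analysis. I-131 activity on the right lenses (artificial tears) is compared with the left (no tears) by a paired t-test on log-transformed four-day AUC, two-sided at 0.05. Obstruction does not appear there.

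Section 2.1 sets the sample at 5 patients, with no justification, and reports the "incidence of radioactive iodine associated nasolacrimal duct obstruction to be around 3 to 4.6" per cent. It also says of dose: "Doses of 150 mCi or more, which are frequently used in the treatment of thyroid carcinoma, have been found to significantly increase" the risk of obstruction. Section 3.1 enrols only patients treated at 150 mCi or more.

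**The concern.** The primary endpoint is the result by which a trial is judged. Here it contradicts the objectives and has no planned analysis. Its event is also not fully defined: Section 1.2 follows symptoms, while Section 5.1.1 refers first to obstruction and then to dysfunction on irrigation. The plan does not say how these combine or whether findings are recorded for each eye. A record kept only per patient could not support a treated-versus-control comparison, because each patient has one eye of each kind.

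Two errors could follow. A finding of no obstruction, which is likely whether or not the drops work, could be presented as evidence of prevention, since Section 1.2 sets out to draw that conclusion. And with two competing primary outcomes on paper, either could be put forward as primary once the data are seen.

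**Working it through.** **Inputs.** N = 5 patients, hence 5 treated eyes, 5 control eyes and 10 eyes in all (Section 2.1). Incidence p = 3% to 4.6% (Section 2.1). The document does not say whether this is per patient or per eye, over what period, or how it was ascertained, so both units are shown. The document gives no derivation of the sample size, so there is no figure to reproduce.

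**Expected events, N × p.** Per patient: 5 × 0.03 = 0.15 and 5 × 0.046 = 0.23. Per eye: 10 × 0.03 = 0.30 and 10 × 0.046 = 0.46.

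**Chance of no event, (1 − p)^N.** The per-eye column assumes independent eyes. Doubled and tripled rates allow for the higher risk at the enrolled doses; the multiples are assumptions.

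| Incidence | None in 5 patients | None in 10 eyes |
|---|---|---|
| 3% / 4.6% (as quoted) | 0.97^5 = 86% / 0.954^5 = 79% | 0.97^10 = 74% / 0.954^10 = 62% |
| 6% / 9.2% (double) | 73% / 62% | 54% / 38% |
| 9% / 13.8% (triple) | 62% / 48% | 39% / 23% |

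**Rate at which at least one event becomes more likely than not.** Per patient: 1 − 0.5^(1/5) = 12.9%, and 12.9 / 4.6 = 2.8 times the highest quoted figure. Per eye: 1 − 0.5^(1/10) = 6.7%, about 1.5 times.

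**Zero or one event at the extreme.** At 13.8% in 10 independent eyes: 0.862^10 + 10 × 0.138 × 0.862^9 = 0.226 + 0.363 = 59%.

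**What the likely results would show (exact two-sided 95% intervals).** For 0 of 5 the upper end is 1 − 0.025^(1/5) = 52%. For 0 of 10 it is 1 − 0.025^(1/10) = 31%, if eyes are independent. For 1 of 5 the interval runs from 0.5% to 71.6%.

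**If obstruction were tested.** The plan names no test, so this is illustrative. With an exact two-sided McNemar test, all 5 pairs discordant in the same direction give p = 2 × 0.5^5 = 0.0625, so 0.05 cannot be reached. The mid-p version (0.031) and the uncorrected McNemar test (0.025) can fall below 0.05, but only in that same extreme result.

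**Scale.** Take 3% or 4.6% as the control-eye rate, and suppose the drops prevented every obstruction. The exact test then needs at least 6 discordant pairs, and 80% power needs 263 or 171 pairs.

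**The case against.** The strongest reply is that this is a labelling slip in a small pilot. Section 1.1, the statement of purpose in Section 2.1 and Section 6 all point to the tear radioiodine level; only Section 5.1.1 differs, so a careful reader can guess what was meant. That is good evidence about which passage is out of line, but it does not remove the contradiction. Nothing in the document settles it, and only the sponsor can confirm the intent.

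A second reply is that events may be commoner here than the quoted incidence suggests, because doses are high and every patient is irrigated every 8 months, whereas the ascertainment behind the quoted figure is unknown. This has some force. On the per-eye reading at triple the quoted rate, the chance of no event falls to 39% to 23%, so a wholly event-free trial is less certain than the per-patient figures suggest. The conclusion survives: zero or one event remains more likely than not at that extreme, and the intervals stay too wide to show prevention.

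Third, the event is not wholly undefined, since Section 5.1.1 gives the method, interval and duration. That is fair. What is missing is narrower: which irrigation finding counts, whether it is recorded by eye, and how symptoms relate to it.

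Finally, changing the primary label may come after lens results were known, because most of Section 6 is in the past tense. This is a real risk, and it is why the amendment should be dated and disclosed.

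**Conclusion.** The concern holds and must be fixed. The reversed ranking and the missing analysis are plain on the page and rest on no assumption. The lack of information rests on 5 patients and the document's own 3 to 4.6%. The unit of that rate, the independence of eyes and any increase in risk at higher doses are assumptions, and varying them changes the chance of an event-free trial but not the conclusion. In no version considered could obstruction in 5 patients support or refute a preventive effect. The McNemar floor is a side point and the finding does not depend on it.

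**What to change.** Subject to the sponsor confirming the intended ranking, amend Sections 1.2, 5.1.1 and 6 as follows.

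- **Primary endpoint (5.1.1):** the right-versus-left comparison of log-AUC of lens I-131 activity, matching Sections 1.1 and 6, reported as a geometric mean ratio with its 95% confidence interval.
- **Secondary endpoint (5.1.1 and 6):** duct obstruction, descriptive, with no hypothesis test. State which irrigation finding is an event, record it for each eye at the 8, 16 and 24 month irrigations already planned, and give counts with exact 95% intervals. Keep symptoms as supportive data.
- **Objective 1.2.1:** reword it to describing the occurrence of obstruction by eye, and state that the trial cannot support a conclusion on prevention.
- **Timing:** date the amendment and say whether lens results were known on that date. If they were, disclose this when reporting and cite objective 1.1.1 as the statement the label was corrected to match.

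The cost is an amendment and a disclosure, with no added patients, visits or procedures. There are three drawbacks. The claim becomes more modest. If lens results were already known, the relabelled primary carries less confirmatory weight. And the replacement is itself weak: with 5 pairs the two-sided paired t-test reaches 80% power only at a standardised paired difference of about 1.7, and has 40% power at 1.0.

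### With the right eye treated in every patient and no masking described, irrigation and scan readings are open to expectation, and one false-positive call would exceed the obstructions expected

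*Combined protocol and SAP*

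**What the plan says.** - **Allocation (Section 2.1).** The plan states "We will recruit a total of 5 patients who wear bilateral disposable contact lenses" and will "have them self-administer preservative free artificial tears in the right contact-wearing eye (left contact-wearing eye will receive no tears". The treated side is the same in everyone, and the control eye gets no placebo drop.
- **Irrigation (Section 5.1.1).** "The primary endpoint will be to assess for the development of nasolacrimal duct obstruction over two years in 8 month intervals". On method: "Every 8 months, each patient will be assessed in the ophthalmology clinic for nasolacrimal duct dysfunction via tear duct irrigation". The section does not say who performs the irrigation, what that person knows, what counts as a positive result, or whether each duct is graded separately.
- **Scans (Section 5.1).** "We will analyze the routine images for localization of radioiodine in the intranasal and nasolacrimal duct regions". No masked or independent reader and no reading rule is given. Section 5.1.2 repeats the purpose without adding either.
- **Incidence (Section 2.1).** "Prior studies have estimated the incidence of radioactive iodine associated nasolacrimal duct obstruction to be around 3 to 4.6" per cent. The same paragraph says that doses of 150 mCi or more "have been found to significantly increase" the risk, without giving a rate. Section 3.1 makes that dose an entry criterion.
- **Analysis (Section 6).** Right and left are compared only for radioiodine on the lenses, which Section 5.1.1 has measured in a well counter. No analysis of obstruction or of the images is described.

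**The concern.** The outcome of an irrigation and the presence of uptake in a duct region both call for a judgement, and the plan sets no threshold to limit it. Because the side is fixed, knowing the protocol amounts to knowing the allocation of every patient at every visit. Section 2.1 also states the expectation openly: less iodine in the tears should mean less obstruction. An unmasked assessor with that expectation could call a doubtful left duct obstructed or a doubtful right duct patent, and both errors favour the drops.

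What is at stake is the credibility of each call. Very few true obstructions can be expected, so any that are reported will be read case by case by side, and the preventive aim in Section 1.2.1 invites that reading.

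**Working it through.** The documents give no event count, power or sample-size derivation, so there is no figure of the plan's to reproduce.

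**Inputs.** 5 patients, 10 ducts, 5 per side (Section 2.1). Incidence p = 3% to 4.6% (Section 2.1); no follow-up time and no per-patient or per-duct basis is given, so both bases are shown. Two years at 8-month intervals gives 24 / 8 = 3 visits, hence 10 × 3 = 30 duct readings if everyone attends and both ducts are irrigated.

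**Expected true obstructions, n × p, and chance of at least one, 1 − (1 − p)^n**

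| Basis | n | Expected | Chance of at least one | One false positive ÷ expected |
|---|---|---|---|---|
| Per patient | 5 | 0.15 to 0.23 | 14.1% to 21.0% | 6.7 to 4.3 |
| Per duct | 10 | 0.30 to 0.46 | 26.3% to 37.6% | 3.3 to 2.2 |

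The per-duct row treats the two ducts of a patient as independent.

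**Higher risk at the enrolled dose.** The documents give no rate at 150 mCi or more. Doubling, as an assumption, gives p = 6% to 9.2%: 0.30 to 0.46 expected per patient and 0.60 to 0.92 per duct. On the per-duct basis the ratio falls to 1 / 0.60 = 1.7 and 1 / 0.92 = 1.1. The expected count reaches 1 only at p = 1/5 = 20% per patient or 1/10 = 10% per duct.

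**How few misreadings would matter.** Let e be the false-positive rate per reading (an assumption; the documents give none). Expected false calls are 30 × e: 0.30 at 1%, 0.60 at 2% and 1.5 at 5%. At 5% the chance of at least one is 1 − 0.95^30 = 78.5%, treating readings as independent. False calls equal true obstructions (per-duct basis) when e = 0.30/30 = 1.0% to 0.46/30 = 1.5%. These are false calls of any cause, not only those due to expectation.

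**What masking cannot do.** If all 5 patients had exactly one obstructed duct, always on the untreated side, the exact two-sided sign test would give 2 × (1/2)^5 = 0.0625, above 0.05.

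**The case against.** The strongest reply is that the plan's one specified comparison is hardly exposed. Tear iodine is the primary objective in Section 1.1.1 and the only outcome analysed in Section 6, and it comes from an instrument. This stands. The point is limited to irrigation and imaging and does not call the iodine result into question. It does not vanish, because Section 5.1.1 still names obstruction as primary.

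Other parts of the reply also stand:

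- A reader might infer that the assessors know the treated side, or are the investigators themselves. Section 5.1.1 says only that the visits are in the ophthalmology clinic. Section 5.1 implies that the study team reads the scans but not what the reader knows.
- A reader might infer that a planned right-left test of obstruction is biased. Section 6 contains no such test.
- A reader might take the ratios, or the 20-point change in one side's rate from a single duct (1 of 5), as the size of the bias. The change follows from having 5 ducts per side, whether or not the call is masked or correct. The upper ratios hold only if the incidence is per patient.
- Calling an obstructed right duct patent requires a true obstruction first, which is unlikely here. Only the false-positive error can occur freely.
- The scans are taken at about 1 week and add nothing to the obstruction count.
- Describing the visit per patient is ordinary wording. It does not show that ducts will not be graded separately; it only leaves that unsecured.

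None of this supplies masking or a grading rule where the plan has none.

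**Conclusion.** The point holds in limited form. A fixed treated side with no masking leaves two judged outcomes, irrigation and duct uptake on the scans, open to expectation by anyone who knows the protocol. A single false-positive irrigation call would be about 2 to 7 times the expected number of true obstructions at the plan's own incidence. It would still slightly exceed that number on the per-duct basis if the rate were doubled.

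This rests on the 3 to 4.6% figure applying over the two-year follow-up, per patient or per duct, and on an inference about what assessors would know. It does not show that any reading will be wrong or how large a bias would be.

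**What to change.** 1. **Sections 2.1 and 5.1:** assign the treated eye from a concealed random list, balanced as far as 5 patients allow (3 and 2), in place of always the right. This matters most, because not telling an examiner the side masks nobody who knows a fixed right-eye rule.
2. **Section 6:** restate the lens comparison as treated versus untreated eye, and state that obstruction is reported descriptively, by duct.
3. **Section 5.1.1:** have existing clinic staff who have not seen the allocation irrigate both ducts and grade each separately (patent, partial, complete). Record the grades before the allocation is opened, and ask patients not to disclose the side.
4. **Section 5.1:** have the head images cropped and randomly mirrored before they are read for duct uptake.
5. **Lens containers:** coding is optional, since the well counter gives an instrument reading.

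The cost is a short allocation list, relabelling of images and minor scheduling, so that someone unaware of the allocation performs each irrigation. No visit, patient or additional post is needed. Patients will still know which eye had drops, so symptoms they report remain unmasked.
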